Hypothesis: Patients who receive the ADL-enhanced program plus usual rehabilitation therapy will show greater improvements in the Motor Skills scores of the Assessment of Motor and Process Skills (the primary outcome), Self-care items in the Outcome and Assessment Information Set (clinical outcome), and Activity Measure for Post-Acute Care Home Health Short Form (patient-reported outcome) at treatment completion and less decline at 1-month and 3-month follow-up than usual rehabilitation therapy.

Secondary Objectives.

Secondary objective 1: To estimate the preliminary effect of the ADL-enhanced program on improving physical functioning at treatment completion and one month after the completion.

Hypothesis 1: Patients who receive the ADL-enhanced program plus usual rehabilitation therapy will show greater improvements in the Box and Block Test (upper extremity physical function), Jebsen Hand Function Test (upper extremity physical function), Timed-Up-and-Go Test (lower extremity physical function), and Short Physical Performance Battery (lower extremity physical function) at treatment completion and less decline at one-month follow-up than usual rehabilitation therapy.

Secondary objective 2: To assess the completion, satisfaction, and adverse event rates of the ADL-enhanced program.

Hypothesis 2a: We hypothesize that the program completion and satisfaction rates will be greater than 75%.

Hypothesis 2b: Fewer patients who receive the ADL-enhanced program will have hospitalizations, emergency room visits, and falls than patients who receive usual rehabilitation therapy at 1-month and 3-month follow-up.

Background and Rationale

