Saint Louis University Mental Status Exam	x			

Patient demographic background and medical info from self-report as well as chart review	x			
Patient satisfaction survey		x		
Adverse events (hospitalization, falls, emergency room visits)		x	x	x

+: The end of ADL-enhanced program, the last home visit of usual care, or 6 weeks from the baseline assessment, which occurs last.

Study visit schedule.

Description of Evaluations.

Screening evaluation.

The screening will occur over the phone within three business days after a home health care provider has mentioned the study opportunity to the patient and received verbal permission from the patient for the research coordinator to contact him/her. The research coordinator will follow a phone script approved by the UF IRB for this phone screening. The coordinator will obtain a verbal permission prior to proceeding with screening questions from the potential research participant after a brief introduction of the study. These screening questions are:

1. Are you aged 65 years or above?
2. How many medical conditions, including chronic conditions, that you currently have? Examples of the conditions include but not limit to diabetes, heart disease, high blood pressure, joint disease or arthritis, and lung disease.
3. Do you have any of the following conditions?
 - an elective joint replacement surgery in the last month
 - orthopedic or heart surgery in the last month
 - lower extremity amputation
 - currently receiving treatment for cancer
 - an ongoing dialysis treatment
 - a neurologic condition, such as stroke or Parkinson's disease, that significantly limits your movements
 - congestive heart failure that is at the terminal stage

In addition to these questions, the interviewer will administer the "Six-item cognitive screener" to determine the potential participant's cognitive ability. If a participant scores a 4, 5, or 6 on the screener, they will be eligible for the study.

Enrollment, baseline, and randomization.

Enrollment. A patient is considered enrolled in this study when he or she meets the eligibility criteria and signs the informed consent form.

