Randomization. Randomization will occur after the baseline assessment. [name] (Co-I) will generate a randomization list using a computer software and seal the list in opaque envelopes. The on-site research coordinator will open one envelope after a patient has completed the baseline assessments. If the patient is assigned to the ADL-enhanced group, the coordinator will notify the study OT to start intervention.

Post-intervention evaluation.

The satisfaction survey will be given to the patient in the experimental group after the last visit of ADL-enhanced intervention by the research coordinator over the phone.

For the group that will receive the ADL-enhanced program, the post-intervention evaluation conducted by the blinded outcome assessor will occur within seven business days after the completion of the last visit of usual home health rehabilitation therapy or ADL-enhanced intervention, whichever occurs last. For the control group, the post-intervention evaluation conducted by the blinded outcome assessor will occur either 6 weeks after the baseline assessment or after the last usual home health visit, whichever occurs last. Patients will be instructed not to discuss their therapy content with the blinded outcome assessor and vice versa. The following assessments will be administered during the post-intervention evaluation visit.

1. Assessment of Motor and Process Skills
2. Activity Measure of Post-Acute Care Home Health Short Form
3. Jebsen Hand Function Test
4. Box and Block Test
5. Timed-Up-and Go
6. Short Physical Performance Battery
7. Adverse events questionnaire

The research coordinator will extract the patient's OASIS self-care item scores (scores at the start of care and discharge) from medical chart when the patient has been discharged from home health care or 60 days after admission.

One-month follow-up evaluation.

The one-month follow-up evaluation conducted by the blinded outcome assessor will occur within seven business days one month after the completion of the last visit of usual home health rehabilitation therapy or ADL-enhanced intervention (Day 30 post intervention), whichever occurs the last. Patients will be instructed not to discuss their therapy content with the blinded outcome assessor and vice versa. The following assessments will be administered during the one-month follow-up evaluation visit.

1. Assessment of Motor and Process Skills
2. Activity Measure of Post-Acute Care Home Health Short Form

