3. Jebsen Hand Function Test
4. Box and Block Test
5. Timed-Up-and Go
6. Short Physical Performance Battery
7. Adverse events questionnaire

Final evaluation or three-month follow-up evaluation.

The final evaluation will occur over the phone by the research assistant or coordinator within seven days three months after the completion of the last visit of usual home health rehabilitation therapy or ADL-enhanced intervention (Day 90 post intervention). The following assessments will be administered during the final evaluation.

1. Activity Measure of Post-Acute Care Home Health Short Form
2. Adverse events questionnaire

Data analysis plan.

Preliminary analysis. We will compare participant demographics and covariates (e.g., pain levels) between the two groups. Variables with statistically significant differences will be included in the subsequent statistical models as covariates. We will graph spaghetti plots for repeated measurements and examine for outliers.

Data analysis. Since ADL and physical functioning outcomes will be collected over three time points (baseline, post-treatment, one-month follow-up), the mixed-effects linear regression modeling will be conducted to fit the data, in which a random-effects term is included to accommodate within-subject data correlation and a quadratic growth curve is included to describe the temporal trend of the response.

For **Aim 1**, which will estimate the preliminary effect of the ADL-enhanced program on improving ADL, three separate mixed-effects regression analyses will be conducted for the Motor Skills scores of the Assessment of Motor and Process Skills (the primary outcome), the Activity Measure of Post-Acute Care Home Health Short Form, and the OASIS self-care items, in each of which sex, race, age, and other covariates will be included in the model.

For **Aim 2**, which will estimate the preliminary effect of the ADL-enhanced program on physical functioning of the upper extremity and lower extremity, four similar separate analyses will be conducted for the Box and Block Test, Jebsen Hand Function Test, Timed-Up-and Go, and Short Physical Performance Battery.

For **Aim 3**, the program completion rate and satisfaction rate will be compared to the benchmark, 75%. Fisher's Exact Test will be performed to compare the proportion of patients who experience adverse events of hospitalization, emergency room visits, or falls (adverse event rate) between the two groups.

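### Hypothesis 2b times the adverse event comparison at the 1-month and 3-month follow-ups only, and Aim 3 sets no window, so events during programme delivery may go uncounted

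*Combined protocol and SAP*

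**What the plan says.** All references are to the combined protocol and SAP.

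- **Secondary objective 2** reads "To assess the completion, satisfaction, and adverse event rates of the ADL-enhanced program". It sets no time window, and neither does the third aim in the Abstract.
- **Hypothesis 2b** reads "Fewer patients who receive the ADL-enhanced program will have hospitalizations, emergency room visits, and falls" and places the comparison with the control arm at two contacts: "than patients who receive usual rehabilitation therapy at 1-month and 3-month follow-up".
- **Section 6.1, Schedule of Evaluations.** The row beginning "Adverse events (hospitalization, falls, emergency room visits" is marked at three contacts: post-intervention, one month and 3 months. The footnote puts the post-intervention visit at the latest of programme end, last usual-care visit, "or 6 weeks from the baseline assessment, which occurs last".
- **Post-intervention evaluation.** The list of assessments ends with "7. Adverse events questionnaire". The one-month and three-month lists also include that questionnaire.
- **Data analysis plan, Aim 3.** "Fisher's Exact Test will be performed to compare the proportion of patients who experience adverse events of hospitalization, emergency room visits, or falls". No visit, window, denominator or rule for accumulating events is given.

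**The concern.** One endpoint is handled in three ways: two time points in the hypothesis, three in the schedule, none in the analysis. An analyst looking for a window finds one only in Hypothesis 2b, and that window starts after the programme has ended.

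The interval left out is the one in which the intervention is delivered. Under the restorative approach, patients practise graded household tasks at moderate exertion, 15 to 20 minutes per task, with options such as a weighted cuff, greater speed or overhead reach. They are at least 65 years old and have three or more comorbidities. A fall or admission caused by the programme would be expected mainly in this period. A report of fewer events drawn only from the later period would say nothing about it.

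With no window fixed in Aim 3, the choice could also be made after the data have been seen.

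**Working it through.** The documents give no event rate, alpha or power target for adverse events, so there is no figure to reproduce. The check is mainly a comparison of texts.

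**Step 1: time points named for adverse events**

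| Place | Post-intervention | 1 month | 3 months |
|---|---|---|---|
| Secondary objective 2; Abstract, third aim | no window | no window | no window |
| Hypothesis 2b | not named | named | named |
| Section 6.1 schedule | marked | marked | marked |
| Visit lists | listed | listed | listed |
| Aim 3 analysis | no window | no window | no window |

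**Step 2: is the omission in Hypothesis 2b likely to be read as meant?** The primary hypothesis names treatment completion and then the 1-month and 3-month follow-ups. Hypothesis 1 names treatment completion and then the one-month follow-up. Of the hypotheses that compare the arms, only 2b leaves treatment completion out. A reader going by this pattern could reasonably take the omission as intended.

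**Step 3: does the 1-month report reach back into the programme?** The recall period of the adverse events questionnaire is not stated, so the text does not settle it.

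**Step 4: share of observation time at issue**

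- Minimum treatment period (section 6.1 footnote): 6 × 7 = 42 days.
- Follow-up (final evaluation): 90 days.
- Share: 42 / (42 + 90) = 42 / 132 = 0.318, or 32%.
- The 42 days is a minimum, because the post-intervention visit waits for the latest of three events. If treatment filled the 60-day study period in Adherence Assessment, the share would be 60 / (60 + 90) = 40%.

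**Step 5: illustration only.** Assume a constant hazard, two-sided alpha 0.05, 24 per arm, and 132-day risks of 40% (control) and 20% (experimental).

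- Risks over the last 90 days: 1 − 0.6^(90/132) = 0.294 and 1 − 0.8^(90/132) = 0.141.
- Control patients with an event over the full period: 24 × 0.40 = 9.6. No longer counted: 24 × (0.40 − 0.294) = 2.5.
- Exact Fisher power: 0.236 over the full period, 0.171 over the last 90 days.
- Range: with a hazard ratio of 0.5 and control risks of 20%, 40% or 60%, power is 0.09, 0.18 or 0.29 over the full period, against 0.06, 0.13 or 0.21 over the last 90 days.

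Power is low under every version, so its loss is not the argument.

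**Step 6: would a cumulative test alone show harm?** For scale only, suppose on-programme risks of 30% and 10% and a later risk of 20% in both arms.

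- Cumulative risks: 1 − 0.7 × 0.8 = 0.44 and 1 − 0.9 × 0.8 = 0.28.
- Fisher power at 24 per arm: 0.142.

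The cumulative test would usually miss such a difference, so a separate table for the programme period is needed as well.

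**The case against.** The strongest reply is that nothing is actually excluded. The only stated test is the Fisher test in Aim 3, which is to be run "to compare the proportion of patients who experience adverse events" and limits itself to no visit. Secondary objective 2 is equally open. The timing phrase in Hypothesis 2b could also mean cumulative status as of each contact. A reader might infer that programme-period events definitely drop out of the safety comparison. The documents do not support that, and this part of the objection stands: the events may be left out, depending on which text the analyst follows.

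A second reply is that Hypothesis 2b states an expected benefit, in line with the rationale that preserved ADL lowers admissions, and that a benefit can fairly be looked for after the programme. That is a legitimate reading of the hypothesis. It does not rescue the objective, because no other between-arm comparison of adverse events is specified. If 2b concerns later benefit only, the events of the delivery period have no stated analysis.

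A third reply is that this is a 48-patient pilot, the endpoint is secondary, and the data are collected regardless. All true. This limits the weight of the point and also makes the correction cheap.

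**Conclusion.** The point holds in conditional form. The adverse event window differs between hypothesis and schedule and is undefined in the analysis. If Hypothesis 2b is followed as worded, falls, emergency room visits and hospitalizations during programme delivery are left out, and the comparison does not answer Secondary objective 2. The time at issue is at least 42 of 132 days (32%), taking the 6-week minimum and 90 days of follow-up.

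Two further inferences should not be drawn. A reader might argue that patients hospitalised during the programme are likely to be lost later, so that a follow-up-only comparison is made among those who came through the risk period. The documents give no data on loss and define no analysis set for Aim 3, and the three-month contact is by phone. A reader might also rest the case on lost power. The event rates behind any such figure are assumed, and the change is immaterial in a trial of this size. The gain from correction lies in counting the delivery period and showing it separately.

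**What to change.** Use the same definition in Hypothesis 2b and in Aim 3: the Fisher comparison is the proportion of all randomised patients with any hospitalization, emergency room visit or fall from randomisation through the Day 90 contact, counting events reported at the post-intervention visit.

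Add one descriptive table of the same events by arm for the programme period, from randomisation to the post-intervention visit. Give the days of observation in each arm, since the date of that visit is set by different milestones in the two arms.

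State the recall period of the questionnaire at each contact, and say how a patient with a missed contact is counted. If events have already been compared between arms, date the change and say so.

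The cost is a few sentences and one table. No visit, instrument or treatment procedure changes, and the schedule already provides for collecting the data.

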Study design overview. This is a single-blinded, pilot randomized controlled trial of 48 Medicare patients referred to HHC for skilled rehabilitation services. Twenty-four patients will be randomly assigned to the treatment-as-usual arm and receive usual rehabilitation services. The other 24 patients in the experimental arm will receive the ADL-enhanced program in six OT visits as well as usual rehabilitation services.

Selection and Enrollment of Participants

Participants will be recruited from partnered home health agencies

Inclusion criteria. Patients are eligible to the study if they are:

- (1) \geq 65 years of age,
- (2) Medicare beneficiaries,
- (3) referred for skilled rehabilitation services; and
- (4) diagnosed with three or more comorbidities.

Exclusion criteria. Patients are ineligible if they have contraindications for moderate-intensity exercise, which include:

- acute fractures with surgical or weight-bearing restrictions,
- elective joint replacement surgery,
- lower extremity amputation,
- active treatment for cancer diagnosis,
- on-going dialysis treatment,
- acute cardiac surgery,
- acute stroke or a major neurologic disorder limiting motor movements,
- terminal stage of congestive heart failure,
- a referral to hospice care, or
- severe cognitive deficits limiting verbal communication.

Enrollment Procedures.

Screening procedure. The home health care team will obtain verbal permission from new patients to allow the research coordinator to contact and screen the new patients via phone. The coordinator will record the screening results (fail or pass) on a screening log. The coordinator will call the eligible patient, verify the eligibility, and introduce the study.

Consent procedure. The coordinator will then conduct a recruitment home visit to the eligible patient and obtain consent at the end of the visit. If the patient does not provide consent during the recurrent home visit but decides to participate in the study afterwards, a study outcome assessor will obtain consent at the beginning of the baseline assessment visit. Reasons of rejection will be recorded.

Patients who are eligible and agree to participate will be referred to the study outcome assessor, who will schedule the patient within 48 hours to obtain the consent, if not yet obtained by the research coordinator, and complete the baseline assessments (ADL and physical functioning assessments) at the participant's home. The assessor will be blinded to group assignments.

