
Randomization procedure. [name] (Co-I) will generate a randomization list using a computer software and seal the list in opaque envelopes. The on-site research coordinator will open one envelope after a patient has completed the baseline assessments. If the patient is assigned to the ADL-enhanced group, the coordinator will notify the study OT to start intervention.

Study Intervention.

Description of ADL-enhanced intervention. The experimental arm will receive the enhanced-ADL program in 6 home visits from a study OT in addition to usual rehabilitation therapy. The 6 study visits will be delivered over

a 6-week period. The study OT visits will occur separately from usual therapy visits. If the patient cancels a study OT visit, the visit will be rescheduled. The patient will have a 21-day window to resume the intervention. The study OT will apply the compensatory approach in the first 2 visits and the restorative approach in the other 4 visits. Both approaches respect and incorporate the patient's activity preferences in the patient-centered treatment plan. The study OT and the patient collaborate to identify and address ADL tasks that are important and meaningful for the patient's independence.

Compensatory approach procedures. The study OT will conduct a semi-structured interview in the 1st visit to understand the patient's daily routine and to identify two or three ADL tasks that are meaningful but difficult for the patient because of reduced intrinsic capacity. The study OT and the patient collaboratively decide which energy conservation techniques to apply. The patient practices applying these techniques to the selected ADL tasks. The patient is instructed to carry out these ADL tasks with practiced energy conservation techniques until the next visit.

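### The coordinator role that recruits patients also opens the allocation envelopes, so a recruiter may know earlier assignments, and no safeguard against anticipating later ones is described

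*Combined protocol and SAP*

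**What the plan says.** **Recruitment.** Under Screening procedure, "The coordinator will call the eligible patient, verify the eligibility, and introduce the study". Under Consent procedure, "The coordinator will then conduct a recruitment home visit to the eligible patient and obtain consent at the end of the visit". For patients who decide later, "a study outcome assessor will obtain consent at the beginning of the baseline assessment visit".

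**Allocation.** Under Randomization procedure, a Co-Investigator "will generate a randomization list using a computer software and seal the list in opaque envelopes". Then: "The on-site research coordinator will open one envelope after a patient has completed the baseline assessments". Next: "If the patient is assigned to the ADL-enhanced group, the coordinator will notify the study OT to start intervention". The Randomization paragraph under Enrollment, baseline, and randomization repeats this, adding only "Randomization will occur after the baseline assessment".

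**Arm sizes.** Study design overview states: "Twenty-four patients will be randomly assigned to the treatment-as-usual arm and receive usual rehabilitation services". The other 24 of the 48 go to the experimental arm.

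**Later contacts.** Under Post-intervention evaluation, the coordinator phones experimental-arm patients for the satisfaction survey. The three-month call may be made by a research assistant or the coordinator.

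**Not stated.** The plan does not give the type of randomization, block size, envelope numbering, custody of unopened envelopes or an opening log. It does not say whether the scheme is hidden from the coordinator, or whether one person fills the coordinator role throughout. Only the outcome assessor is described as blinded.

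**The concern.** Opening the envelope after baseline keeps that patient's baseline scores independent of the assignment. It does nothing for the patients who follow. A recruiter who has opened the earlier envelopes carries that knowledge into the next screening call and recruitment visit. If the list is restricted, earlier assignments carry information about later ones.

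The recruiter keeps some discretion: how warmly the study is presented, when within the allowed window the visit is booked, and how borderline self-reported answers are read (for example, whether a neurologic condition limits movement enough to exclude). If any of these came to depend on the expected arm, the groups could differ in motivation or frailty. Motivation is not among the baseline measures, so the covariate adjustment in the Data analysis plan could not fully repair such a difference. The trial's main product is a preliminary effect estimate from 24 patients per arm, where a few steered patients could matter.

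A second gap does not depend on prediction. The text says that one envelope is opened, not that it is the next in a numbered series, and describes no record tying an envelope to a patient. An envelope taken out of order would leave no trace.

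**Working it through.** The documents give no figure for predictability, so there is none to reproduce. The only internal check is 24 + 24 = 48, which agrees.

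**Inputs.** Total 48 and planned arms of 24 and 24, from Study design overview. Block sizes are my assumptions, because the plan gives none.

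**Is a restricted list likely?** Simple randomization gives exactly 24:24 with probability C(48,24)/2^48 = 0.115. The planned sizes therefore suggest a restricted list, but do not prove one.

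**Guessing model.** One recruiter has seen all earlier assignments, knows the scheme, guesses the arm with more places left and tosses a coin at ties. For a block of 2n patients:

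- expected correct guesses = n + 2^(2n−1)/C(2n,n) − 1/2
- expected assignments known with certainty = 2n/(n+1)

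Worked examples:

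- One 24:24 list (n = 24): 24 + 4.36 − 0.5 = 27.9, and 27.9/48 = 58.1%.
- Blocks of 6 (n = 3): 3 + 32/20 − 0.5 = 4.1, and 4.1/6 = 68.3%.
- Blocks of 4 (n = 2): 2 + 8/6 − 0.5 = 2.833, and 2.833/4 = 70.8%.
- Blocks of 2 (n = 1): 1 + 2/2 − 0.5 = 1.5, and 1.5/2 = 75.0%.

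Scaled to 48 patients:

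| Scheme | Correct guesses | Per cent | Gain over 24 | Known with certainty |
|---|---|---|---|---|
| Simple | 24.0 | 50.0 | 0 | 0 |
| One 24:24 list | 27.9 | 58.1 | 3.9 | 1.9 |
| Blocks of 12 | 30.9 | 64.3 | 6.9 | 6.9 |
| Blocks of 8 | 32.0 | 66.6 | 8.0 | 9.6 |
| Blocks of 6 | 32.8 | 68.3 | 8.8 | 12.0 |
| Blocks of 4 | 34.0 | 70.8 | 10.0 | 16.0 |
| Blocks of 2 | 36.0 | 75.0 | 12.0 | 24.0 |

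**Why these are upper bounds.** The model places the guess immediately before each assignment. In the plan, the coordinator acts at screening or at the recruitment visit, which is up to five business days after the patient passes screening. Baseline may follow up to seven business days after that visit, and the assessor schedules it. With several patients in process at once, the coordinator may not know which place on the list a given patient will take.

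**The case against.** A reader might infer that the recruiter can simply predict the next assignment. The documents do not support that. Prediction needs a restricted scheme that the recruiter knows or can infer, and none is described. The 24 and 24 are planned arm sizes, and the text does not say that the list is forced to them. Under simple randomization, full knowledge of past assignments gives no gain.

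A reader might also infer that one person opens every envelope and controls recruitment. Recruitment is from several partnered agencies and the text refers to an on-site coordinator, so there may be more than one, each seeing only part of the list. The home health team makes first contact, screening follows an approved script with a numeric cognitive cut-off, visits have time windows, and a screening log and refusal reasons are kept. The assessor takes some consents. These limits narrow the room for steering and may help to detect it, but they do not prevent it. Patients who consent late have still been screened and visited by the coordinator.

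Nor do the documents support any figure for how many patients would be steered or how far the effect estimate would move. The current patient's allocation is formally concealed, because someone else seals the envelopes and they are opened only after consent and baseline.

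All of this stands. It leaves the stated overlap of roles in place, and it leaves envelope order unauditable on the text as written.

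**Conclusion.** The concern holds in a limited form. The plan assigns recruitment and envelope opening to the same unblinded role and describes no safeguard between them. Where one person fills that role, earlier assignments are known while later patients are approached. The possible gain in guessing ranges from nothing (simple randomization) to 12 extra correct guesses in 48 (blocks of 2). That range assumes a single recruiter, full knowledge of the scheme and one patient in process at a time, so it shows what the text leaves open and does not estimate bias. The gaps in numbering and logging remain under any scheme. The point merits an amendment because the remedy is cheap. It is not evidence that the comparison is invalid, and no sample-size figure changes.

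**What to change.** Amend Randomization procedure and the matching Randomization paragraph:

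- Once the assessor confirms that baseline is complete, a team member who does not recruit logs the patient ID and releases the next assignment, in list order, directly to the study OT. This could be the Co-Investigator who generates the list, if that person keeps it (the plan does not say), or an electronic module.
- State the randomization scheme in general terms. If blocks are used, vary their sizes and withhold them from the coordinator.
- While recruitment continues, have the research assistant make the satisfaction call and the three-month call. The satisfaction call goes only to the experimental arm, so whoever makes it learns the assignment.
- If envelopes are kept, number them sequentially, have a non-recruiter hold and open them, and write patient ID and date on each before opening.

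The cost is a short amendment that uses roles already in the plan and a delay in assignment of up to about one working day. Some leakage may remain, for instance through the coordinator's chart extraction, so the change reduces the risk without removing it entirely.
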